**Reading Hospital – Tower Health
Research Protocol**

PI Name: [name].

**Study Title: Role of tranexamic acid (TXA) in the reduction of post-operative hematoma
and seroma in patients undergoing panniculectomy or abdominoplasty, a pilot study**

**NCT04902950
February 27, 2020**

Reading Hospital – Tower Health Research Protocol

PI Name: [name].

Study Title: Role of tranexamic acid (TXA) in the reduction of post-operative hematoma and seroma in patients undergoing panniculectomy or abdominoplasty, a pilot study

Other Investigators / Collaborators [name], D.O., [name], D.O., [name]., [name], D.O., [name].

Funding Source(s): Investigators will apply for funding from the Reading Hospital Foundation. If funding from the foundation is unavailable, investigators will seek other funding sources. If no funding is acquired, the investigators will cover the cost of the study drug.

A. SPECIFIC AIMS

We aim to investigate the use of tranexamic acid (TXA) as a hemostatic agent in abdominoplasty/panniculectomy. We believe tranexamic acid to be effective in decreasing hematoma rates and drain output, allowing for earlier drain removal.

B. RESEARCH QUESTION AND HYPOTHESIS

Does the use of TXA soaked sponges decrease hematoma rates and drain output, resulting in earlier drain removal in patients undergoing panniculectomy or abdominoplasty? Comparative outcomes including return to operating room, fluid collection requiring additional procedures (i.e. aspiration or percutaneous drainage), hematoma rates, daily drain output and time to drain removal will be measured between the control group (normal saline) and the experimental group (TXA). We are evaluating the potential for TXA to reduce drain output and decrease time to drain removal.

C. BACKGROUND AND SIGNIFICANCE

The antifibrinolytic drug, tranexamic acid (TXA) has proven to reduce blood loss and transfusion requirements in other fields of surgery including orthopedic, cardiac, craniofacial and gynecologic surgery. Metanalysis performed by Ker et al. concluded that TXA reduced blood loss by 29 percent and the need for blood transfusion by 49 percent over a variety of surgical procedures.¹ Masoomi et al. reviewed 20,130 patients who underwent abdominoplasty from 2007-2011, noting that 9.3 percent required a post-operative blood transfusion.²

TXA has recently gained popularity in the field of plastic and reconstructive surgery.³ Tranexamic acid is a synthetic lysine analogue which inhibits fibrinolysis and thus degradation of fibrin clots by competitively inhibiting the activation of plasminogen to plasmin. By inhibiting plasmin formation, TXA also provides an anti-inflammatory effect, as plasmin is responsible for several inflammatory activities.^{3,4} Austen et al. demonstrated the efficacy of topical TXA in reducing drain output for patient undergoing reduction mammoplasty.⁵

The safety and efficacy of TXA has been well studied.⁶ Historically administered intravenously, TXA is gaining popularity as a topical hemostatic agent. TXA administered topically has similar efficacy as intravenous administration while minimizing systemic exposure.⁶ The Clinical Randomization of an Antifibrinolytic in Significant Haemorrhage-2 trial (CRASH-2) found that the use of TXA provided a significant mortality benefit without an increased risk for thromboembolic events in adult trauma patients.

Reading Hospital – Tower Health Research Protocol

We believe topical TXA will decrease the rate of post-operative hematoma via its hemostatic effects, as well as decrease the overall drain output via its anti-inflammatory properties.

D. RESEARCH DESIGN AND METHODS (including data analysis)

Patients will be evaluated by the plastic surgeon for a symptomatic abdominal panniculus to determine their candidacy for elective or insurance authorized panniculectomy. Panniculectomy is defined as excision of excess lower abdominal skin and subcutaneous tissue. The term panniculectomy is often used interchangeably with abdominoplasty. Candidates for the study will be undergoing excision of excess abdominal skin and subcutaneous tissue with undermining of the abdominal flap to the xiphoid process superiorly and to the costal margin laterally; with or without rectus muscle plication. Signs and symptoms of a symptomatic abdominal panniculus include but are not limited to recurrent skin infections, difficulty with ambulation, interference with voiding or intercourse, as well as chronic lower back pain or difficulty finding appropriately fitting clothing.

Participating providers will include those physicians with operative privileges at Tower Health System Reading Hospital. Candidates for the procedure will be offered participation in the study preoperatively in the office setting by the provider performing the procedure. If they agree to participate, they will be consented appropriately with the attached IRB approved consent in addition to standard surgical consent.

This study will be double-blinded. Participating patients will be randomized to normal saline (control group) or tranexamic acid (study population) on the day of surgery by the pharmacist. All participants will have an order placed pre-operatively for tranexamic acid. Patient assignment will be determined by a random number table. A random number table is a series of digits 0, 1, 2, 3, 4, 5, 6, 7, 8, and 9 arranged randomly in rows and columns. Numbers in the list are arranged so that each digit has no predictable relationship to the digits that preceded it or to the digits that followed it. Each group will have 10 participants. One for each number in the table. Odd numbers will be assigned to the control group (Saline) and even numbers will be assigned to the study population (TXA). The pharmacist will have the table of random numbers and will assign patients appropriately. The pharmacist will send a 100cc bag of plain normal saline or 100cc bag of normal saline mixed with 3g of tranexamic acid. Tranexamic acid is supplied as 1g/10cc. Three grams of TXA will be mixed with 70cc of normal saline for a concentration of 3% and total volume of 100cc, as not to differ from the plain normal saline quantity. Either 100cc of plain normal saline or 100cc of 3% solution of TXA will be placed on the operative field prior to the start of the procedure. The solution will be placed into a sterile bowl on the operative field and three lap sponges will be placed in the solution at the beginning of the procedure. TXA is clear, odorless solution and will be indistinguishable from normal saline to the provider and operating room staff. To ensure the study providers remain blinded the pharmacist will control the randomization.

Each group will have 10 participants. Group 1 will undergo application of three normal saline soaked lap sponges to the surgical site, while Group 2 will undergo application of three TXA soaked lap sponges to the surgical site. After the abdominal skin and subcutaneous tissue is raised, the area will be irrigated, and hemostasis achieved using electrocautery. These steps are currently preformed with every panniculectomy. After hemostasis and irrigation, the soaked lap sponges will be unfolded and placed beneath the two lateral portions as well as the central area of the flap for 3 minutes. The lap sponges will not be “rung out” prior to placement. The time for TXA application is based on previous studies. The lap sponges will be removed after

Reading Hospital – Tower Health Research Protocol

three minutes. The surface area under the flap will be measured from the xiphoid process to the pubis, from the Xiphoid process to each anterior superior iliac spine (ASIS) and across from one ASIS to the other. These measurements will be used to calculate the surface area under the flap. These measurements will only be used in data collection and do not affect the principle aim of the study. The remainder of the surgical procedure will be the same for each patient. As currently practiced, two 15 round Blake drains will be placed for each patient. Patients will stay overnight for routine post-operative monitoring including vital signs and drain output or may be discharged home the same day of surgery if medically fit. Patients will also be monitored clinically at each post-operative visit for signs of post-operative hematoma or seroma.

After discharge, post-operative drain output will be monitored and recorded by the patient on the provided drain documentation sheet. This does not differ from the current standard of care regarding drain output recordings. All patients who receive a post-surgical drain are asked to document output. All patients will be educated on routine drain care and recording drain output prior to surgery, as well as post-operatively. Each patient will be given a standardized form to record their drain output. Post-operative drain output will be assessed during each post-operative visit. Drains will be removed when output is less than 30cc per drain in 24-hour period. Patients will track their 24-hour total drain output by recording the 24-hour total output at 10 am every day. If the output exceeds the drain capacity during the 24-hour interval but before the 10am empty time, the patient will empty the drain when full, record that output, allow the drain output to reaccumulate, and empty-record the drain output again at 10am or again when the output exceeds the drain capacity. The individual outputs recorded during the 24-hour interval will then be totaled to determine one output sum for the entire 24-hour time period between 10am time intervals. Each drain bulb will accommodate a maximum of 60cc of postoperative fluid. When less than 30 cc per drain in 24-hour period, patients will call to schedule drain removal. Drain recording policies do not differ from non-study patients. All post-operative panniculectomy patients are required to record their drain output. Each patient will be evaluated one week, three weeks, and eight weeks following their procedure to assess overall wound healing, post-operative fluid collections, drain output and overall well-being.

Data analysis for this project will consist of several parts. First it is important to analyze differences between the randomized control and treatment arms to test for bias. In order to do this, goodness of fit tests (GOF) will be performed on demographic variables such as age and gender. While the sample sizes are expected to be low, 10 for each arm, nonparametric tests consisting of Fisher's exact for discrete variables and Mann-Whitney U tests for continuous level data will be used. An omnibus p-value of 0.20 will be used to ensure there is no bias present in the samples. Secondly, efficacy analysis will be conducted on the outcome variables (drain output per day, total drain output, etc.) by use of Mann-Whitney U test. Statistically significant findings would be for a p-value less than 0.05 on any test. The samples are not expected to be large enough for the use of parametric measures so non-parametric methods will be used.

With a small sample of 10 patients per arm this analysis is viewed to be exploratory, and there will be no statistical corrections applied for multiple comparisons. Results of the GOF and efficacy analysis will be prepared and placed into tables for each group. In addition to the analysis mentioned above, power analysis will also be used to calculate the observed power for those tests with significant differences as well as to determine a sample size for those efficacy endpoints that did not achieve statistical difference. These power estimates will accompany the results in a separate table. Power analysis will be based on single tail alternative hypothesis with a power (1-B) of 80 percent and a p-value of 0.05. As this is an exploratory study, there will

Reading Hospital – Tower Health Research Protocol

be no interim analysis for efficacy or futility. The trial will be stopped after inclusion of twenty patients.

E. PROTECTION OF HUMAN SUBJECTS

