1. RISKS TO THE SUBJECTS

a. Human Subjects Involvement and Characteristics

- Double-blind Prospective Randomized Control Trial
- Female or male patients 18 years or older
- Patients undergoing panniculectomy and agreeable to participate in the trial will be randomized to normal saline vs TXA
- Daily drain output will be monitored and recorded for each patient
- Rate of post-operative hematoma/seroma will be assessed by clinical evaluation to include palpation for ballotable fluid collection and assessment of skin for a shiny/tight appearance suggestive of an underlying fluid collection.
- Prisoners, pregnant or nursing women, persons under the age of 18, persons with preexisting coagulopathy, ongoing venous or arterial thrombosis, history of cerebral vascular accident, uncontrolled seizure disorder, documented administration of daily antiplatelet or anticoagulation (e.g. ASA, NSAIDs, Warfarin) or documented allergic reaction to tranexamic acid will be excluded from the study
- Patients can withdraw from the study at anytime

b. Sources of Materials

- All patient charts will be kept confidential, in compliance with HIPPA regulations
- All patient information will be stored on a password protected computer
- Normal saline and tranexamic acid are both products currently in use at the hospital in other plastic surgery procedures. They are indistinguishable in appearance, texture and odor; therefore, making them ideal substances for a double-blinded investigation
- No specimens will be stored

c. Potential Risks

- Potential risks include those risks associated with any surgical procedure.
- Patients will be monitored under standard operative protocols
- Although, the risks of topical use of TXA are not well known, there are known risks from oral and intravenous use. Those risks include:
 - o Allergic reaction
 - o Convulsions have been reported in association with intravenous tranexamic acid treatment in patients undergoing cardiovascular procedures
 - o Retinal changes have been documented in some animals receiving intravenous TXA for extended periods of time (days to weeks)
 - o Intravenous administration of tranexamic acid may cause dizziness
 - o Gastrointestinal disturbances may occur with intravenous administration

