4. IMPORTANCE OF THE KNOWLEDGE TO BE GAINED

- This study allows us to investigate additional methods to achieve low drain outputs in panniculectomy. The knowledge gained from our proposed study will be applicable to patients undergoing panniculectomy. In addition, this method of achieving hemostasis may lead to further research studies for various other surgical procedures.

5. SUBJECT SAFETY AND MINIMIZING RISKS (Data and Safety Monitoring Plan)

Subject safety will be monitored by the physician performing the procedure.

- Subjects will be monitored for allergic reaction, wound healing complications, venous thromboembolism, drain output, and time to drain removal.
- Subjects will be monitored during their overnight hospital stay, if overnight admission is deemed appropriate. Participants will also be evaluated at each follow-up visit. Patients will be scheduled for follow-up at one week, three weeks, and eight weeks following their procedure.
- The physician performing the procedure will be responsible for the monitoring and evaluating patients postoperatively.
- This investigational study aims to assess for any difference in drain output, time to drain removal or return to the OR for hematoma or seroma evacuation.

F. REFERENCES/LITERATURE CITATIONS

3. Reed and Woolley. Uses of tranexamic acid. Continuing education in anaesthesia, Critical Care & Pain. 2015; 15(1):32-37.

Reading Hospital – Tower Health Research Protocol

6. Rohrich RJ and Cho MJ. The role of tranexamic acid in plastic surgery: review and technical considerations. *Plast Reconstr Surg.* 2018 Feb; 141(2):507-515.

G. CONSULTANTS

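### The blinding order names tranexamic acid for every participant, so the chart of a saline control can mislead a clinician outside the study, and the protocol gives no route to check the assignment

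*Combined protocol and SAP*

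**What the plan says.** Section D declares the blind ("This study will be double-blinded") and has patients randomized "on the day of surgery by the pharmacist". For the order that precedes this step, it says: "All participants will have an order placed pre-operatively for tranexamic acid". What is dispensed then depends on the arm: "The pharmacist will send a 100cc bag of plain normal saline or 100cc bag of normal saline mixed with 3g of tranexamic acid".

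The assignment stays with the pharmacist: "The pharmacist will have the table of random numbers and will assign patients appropriately". The stated purpose is masking: "To ensure the study providers remain blinded the pharmacist will control the randomization".

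Section E.5 gives safety to the surgeon: "The physician performing the procedure will be responsible for the monitoring and evaluating patients postoperatively". The events to be watched for there include allergic reaction and venous thromboembolism. Section E.1.c lists "allergic reaction" among the known risks of oral and intravenous tranexamic acid, and says that the risks of topical use are not well known. Section E.1.a excludes anyone with a documented allergic reaction to the drug.

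**The concern.** An order that is the same for everyone is a sensible masking device. The difficulty is that this one names the active drug, so in the control arm it describes something that will not happen. Section E.1.b says both products are already used at the hospital in other plastic surgery procedures, so a tranexamic acid order would look routine and would not by itself suggest a possible placebo.

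Section D allows discharge on the day of surgery, and scheduled visits are at one, three and eight weeks. A reaction or thrombosis between visits may be seen first by clinicians who are not part of the study. If they take the order at face value, they may weigh the wrong exposure during the event. They may also leave an entry, such as a suspected drug allergy, that stays with the patient after the trial. The protocol gives weight to such an entry, since it would exclude a patient from this study.

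**Working it through.** The plan gives no figure to reproduce on this point. The check is mainly a comparison of what each part of the text provides, plus two small calculations.

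**Order against treatment received**

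| Item | Saline arm | TXA arm | Source |
|---|---|---|---|
| Pre-operative order | Tranexamic acid | Tranexamic acid | Section D |
| Bag sent | Plain saline | Saline with tranexamic acid | Section D |
| Order agrees with bag | No | Yes | Comparison |
| Planned patients | 10 | 10 | Section D |

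Charts with an order for a drug not given: 10 / (10 + 10) = 10 / 20 = 50%. The total agrees with the stated stop after twenty patients. The 50% is simply the 1:1 allocation. It counts charts, not misattributed events.

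**Who can find out the assignment**

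- The pharmacist holds the table and makes the assignment (Section D).
- The surgeon monitors safety and is blinded (Sections D and E.5).
- The visible text describes no code-break procedure, patient-level dispensing log, out-of-hours contact, rule for recording or attributing adverse events, or later update of the chart.
- The planned tables by group cover baseline comparisons and efficacy (Section D). No safety table is named.

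**How often the situation could arise**

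The documents give no rate for acute events, so the rate p per control patient is an assumption. The chance of at least one event among 10 controls is 1 − (1 − p)^10:

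- p = 1%: 1 − 0.99^10 = 9.6%
- p = 5%: 1 − 0.95^10 = 40.1%
- p = 10%: 1 − 0.90^10 = 65.1%

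These are chances that a control has an event at all. They are not chances that it is misread, and nothing in the documents allows that second step to be estimated.

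**The case against.** The strongest reply is that the order must be uniform, because one naming saline for controls would reveal the arm. That stands as an argument for uniformity. It does not require the order to name tranexamic acid: an order for blinded study solution, stating both possibilities, is equally uniform and true in both arms.

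A reader might infer that an event in a control will be recorded as a tranexamic acid event. The documents do not support this, for three reasons.

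- They do not give the literal text of the order, say how administration is charted, or contain an attribution rule. An order is also not an administration record.
- The operating physician offers participation, obtains consent and follows the patient, and so knows that saline is possible. Not knowing the arm is what blinding intends, and it applies equally to both arms.
- Section E.2.a puts the signed consent in the chart, so a team with chart access has a sign that the patient is in a study. The consent pages are not in the supplied text and may explain the saline arm or give a contact.

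A reader might also infer that safety data will be misclassified by arm. That does not follow either, because the pharmacist makes each assignment and events can be tabulated by it. This depends on a patient-level record being kept. Section D mentions the random number table but not such a record.

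The lasting allergy entry is likewise a chain of possible steps, none of them documented. What remains is narrower: a clinician outside the study could be misled by the order, the consent form cannot state the individual's arm, and the visible protocol gives no way to learn it.

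**Conclusion.** The point holds as a patient-care and record-keeping weakness that is cheap to remove. If the protocol is followed, a planned 10 of 20 charts will contain an order for a drug that was not given. The size of any resulting harm cannot be stated, because the documents give neither an event rate nor a chance of misreading.

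The conclusion assumes that the order reads as Section D describes it, and that no removed page or attachment supplies a masked label or a code-break route. The missing code-break route would on its own be mainly an omitted detail. It matters more here because the order points readers to one particular exposure. The efficacy comparison is not affected.

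**What to change.** 1. Replace the sentence on the order in Section D with: *All participants will have a pre-operative order for blinded study solution, 100cc (tranexamic acid or normal saline, per pharmacy randomization).*
2. Add that pharmacy keeps a patient-level assignment log, from which a single assignment can be released when it is needed for a patient's care, with the date and reason recorded.
3. Add that charts are updated to the solution received only after the last patient's final visit and data lock. Updating after each patient's own eight-week visit would reveal assignments to surgeons who are still enrolling and assessing others. With a planned 10 per group, known assignments would also make the remaining ones easier to predict.

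The cost is a change of order text and a small pharmacy log. The downside is an occasional unblinding of a single patient, which is recorded.

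### Odd/even allocation from a random number table does not produce the stated 10 patients per arm, and no balancing step is written

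*Combined protocol and SAP*

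**What the plan says.** Everything relevant is in section D, Research Design and Methods, of the combined protocol and SAP.

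- **Allocation method.** "Patient assignment will be determined by a random number table". The table is then described: "Numbers in the list are arranged so that each digit has no predictable relationship to the digits that preceded it", and the same is said of the digits that follow.
- **Allocation rule.** "Odd numbers will be assigned to the control group (Saline) and even numbers will be assigned to the study population (TXA".
- **Arm size, randomization paragraph.** "Each group will have 10 participants. One for each number in the table".
- **Arm size, paragraph on the two groups.** "Each group will have 10 participants. Group 1 will undergo application of three normal saline soaked lap sponges".
- **Arm size, data analysis paragraph.** "While the sample sizes are expected to be low, 10 for each arm". The next paragraph again refers to 10 patients per arm.
- **Total.** "The trial will be stopped after inclusion of twenty patients".

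The pharmacist holds the table and makes the assignments. The text has no blocks, no cap on an arm, no pre-balanced list, no drawing of digits without replacement, and no instruction for what happens when one arm fills.

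**The concern.** The protocol fixes the arm sizes but describes a mechanism that fixes only the total. The parity of independent digits amounts to a coin toss for each patient, so the number assigned to TXA among twenty patients varies by chance. The step that would reconcile rule and size is missing.

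The pharmacist can accept unequal arms, which departs from the stated size, or can force balance by an unwritten method. Two careful pharmacists could run different procedures from the same text. A reader of the final report could not tell from an 8/12 or a 10/10 split whether the plan had been followed.

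At stake are the reproducibility of the allocation, some precision if the arms come out badly unequal, and, if an arm is closed at 10, a run of final patients all in the same group.

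**Working it through.** **Inputs from section D.** Total N = 20. Stated arm size is 10. Odd digits (1, 3, 5, 7, 9) go to saline and even digits (0, 2, 4, 6, 8) to TXA, so each patient's chance of TXA is 5/10 = 0.5. Assumptions: digits are equally likely and all 20 patients are assigned by the rule.

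**Can the stated 10/10 be reproduced?** Not from the rule. The number on TXA is Binomial(20, 0.5), so

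P(10/10) = C(20,10) / 2^20 = 184,756 / 1,048,576 = 0.176.

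**Splits under the written rule.** Relative efficiency against 10/10 is 4·n1·n2/N². The documents give no effect size or SD, so the power column assumes a normal shift of 1.4 SD, chosen because it gives about 80% at 10/10. Power is for the exact two-sided Mann-Whitney test at 0.05, by simulation (200,000 trials per split).

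| Split | Probability | This split or more unequal | Relative efficiency | Power |
|---|---|---|---|---|
| 10/10 | 17.6% | 100% | 1.00 | 80% |
| 9/11 | 32.0% | 82.4% | 0.99 | 81% |
| 8/12 | 24.0% | 50.3% | 0.96 | 80% |
| 7/13 | 14.8% | 26.3% | 0.91 | 77% |
| 6/14 | not split out | 11.5% | 0.84 | 71% |

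Mean relative efficiency over all splits is 1 − 1/20 = 0.95. The first three rows cover 1 − 0.263 = 73.7% of trials and show no meaningful power loss. Power at 9/11 is not truly higher than at 10/10: the exact test is discrete, and its attained level differs slightly between splits.

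**Does the sentence about one participant for each number in the table supply the missing step?** The digits 0 to 9 contain five odd and five even numbers, so one pass gives 5 per group, not 10. Two passes without replacement would give 2 × 5 = 10 per group, but no second pass is written, and drawing without replacement does not fit the description of unrelated digits.

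**Unwritten ways of reaching 10 per arm.**

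1. *Close an arm when it reaches 10.* The chance that closure comes at patient t is 2·C(t−1, 9)/2^t, for t = 10 to 19.
   - Expected forced assignments: 20 × 0.1762 = 3.52.
   - Six or more forced: 2·P(Bin(14, 0.5) ≥ 10) = 2 × 1,471/16,384 = 18.0%.
   - Seven or more forced: 2·P(Bin(13, 0.5) ≥ 10) = 2 × 378/8,192 = 9.2%.
   - The last six patients are all in one arm exactly when six or more are forced, so also 18.0%. With a single random permutation of 10 and 10 the figure is 2·C(14,4)/C(20,10) = 2,002/184,756 = 1.1%.
2. *Enrol until both arms have at least 10.* This needs 20 + 3.52 = 23.5 patients on average, which conflicts with stopping at twenty.

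**Balance over calendar time.** This is the SD of the between-arm difference in mean entry position (places 1 to 20). The variance of the positions is 20 × 21/12 = 35, so a single permutation gives √(35 × (1/10 + 1/10)) = √7 = 2.65. The other rows are from 40,000 simulations each.

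| Method | SD (places) |
|---|---|
| Odd/even rule as written | 2.7 |
| Arm closed at 10 (unwritten) | 4.1 |
| Single permutation of 10 and 10 | 2.65 |
| Permuted blocks 4, 4, 6, 6 in random order | 0.7 |

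**The case against.** The strongest reply is that little depends on equal arms. The plan calls the analysis exploratory, has no sample-size calculation resting on 10/10, and uses tests that are valid at any split. In about three trials in four the split is 8/12 or closer, with no meaningful loss of power. All of this stands and limits the seriousness of the point.

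The calendar-time problem does not belong to the rule as written. Its entry-position SD of about 2.7 is practically that of a single permutation. The 4.1 and the 18.0% arise only if the pharmacist closes an arm. The documents describe no time trend, and over repetitions each patient still has an even chance of either arm, so there is no systematic bias. This also stands: those figures are conditional on a step nobody has written.

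The wording can also be read more kindly. The data analysis paragraph presents 10 per arm as an expectation. The sentence on unrelated digits is a general definition of a random number table and does not forbid using one to prepare a balanced list. The remark about one participant per number may be a garbled reference to such a list. That may well have been the intention, but the procedure still cannot be carried out from the text, and the other two paragraphs state 10 per group without qualification.

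**Conclusion.** The concern holds. The plan states an arm size that its own allocation rule delivers in only 17.6% of trials, and it does not say how the gap is to be closed. This should be corrected before the first patient is assigned, because the allocation procedure of a randomized trial should be reproducible from its protocol.

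The size of the problem is modest. The rule is valid and unbiased and costs 5% in efficiency on average. Under the assumed 1.4 SD shift, power falls visibly only at 7/13 (77%) and 6/14 (71%), against 80% at 10/10; splits of 7/13 or more unequal occur in 26.3% of trials. If an arm is closed instead, the harm is a greater chance that treatment and entry order are entangled in this one trial. The binomial and arm-closing results are exact, given equally likely digits and all 20 patients assigned. The power figures rest on the assumed shift.

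**What to change.** In the randomization paragraph of section D, replace the odd/even sentence and the remark about one participant per number with wording such as:

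> Before the first patient is enrolled, a list of exactly 10 TXA and 10 saline assignments in random order will be generated. The pharmacist will hold the list and use it strictly in sequence.

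The general description of a random number table can then be deleted, or kept only as the means of generating the list. A single random permutation is enough and gives 10/10 whenever all 20 are assigned. Permuted blocks, for example of sizes 4, 4, 6 and 6 in random order, are an optional extra that also limits calendar-time imbalance.

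If simple randomization is preferred, keep the odd/even rule, delete the remark about one participant per number, change both statements of 10 per group to an expected size of 10, and state that the arms may be unequal and that no arm will be closed.

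The cost of the first option is two sentences and a few minutes to generate the list; the second needs only rewording. The pharmacist already controls allocation, so neither needs extra staff or patients, affects blinding, or changes the planned tests.
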